5.3 Demographic and Baseline Characteristics

Summaries of demographics, stratification factors and baseline characteristics will be presented for subjects in the ITT, PITT, P-Safety and Safety populations.

[A] The demographic characteristics include:

- Age (continuous)
- Age category 1
 - < 65 years
 - \geq 65 years
- Age category 2
 - < 75 years
 - \geq 75 years
- Age category 3
 - <65 years
 - 65 to <75 years
 - 75 to <85 years
 - \geq 85 years

- Sex
 - Male
 - Female
 - Not reported
- Ethnicity
 - Hispanic or Latino
 - Not Hispanic or Latino
 - Not Reported
- Race
 - American Indian or Alaska Native
 - Asian
 - Black or African American
 - Native Hawaiian or Other Pacific Islander
 - White
 - Not Reported
 - Other
- Geographic Region
 - Asia
 - Other

Note for this study birth date is not collected but age in years is collected at informed consent.

[B] Categorical summaries of the following stratification factors will be presented as recorded
 (a) in the IRT during randomization (b) on the CRF (c) cross tabulation of all 3
 stratification factors per IRT (d) cross tabulation of all 3 stratification factors per CRF (e)
 cross-tabulation of geographic region and etiology of disease per CRF:

- etiology of disease
 - HBV [with or without HCV]
 - HCV [without HBV]
 - Other
- geographic region (Asia, Other Regions)
- presence of extrahepatic spread of disease and/or macrovascular invasion (Yes, No)

[C] Baseline characteristics include:

- Height in cm— descriptive statistics

- Weight in kg – descriptive statistics
- Body mass index (BMI) in kg/meter², calculated as (weight in kg*10000)/(Height in cm)²
–descriptive summary:
- ECOG PS: 0, 1, Missing
- Smoking history
 - Current
 - Former
 - Never
- Alcohol use – Categorical summary for subjects classified as current user, former user or never will be presented

5.4 Medical History

General medical history data will be coded per MedDRA.

5.5 Cancer History and Current Disease Status

Cancer history and current disease characteristics data collected on the cancer history CRF will be summarized categorically or with descriptive statistics as appropriate for the PITT and ITT populations. The following summaries are planned:

- Diagnosis of carcinoma of HCC by histology or cytology (Yes, No)
- Diagnosis of carcinoma of HCC by imaging (Yes, No)
- Current etiology:
 - Hepatitis B virus (without HCV)
 - Hepatitis C virus (without HBV)
 - Hepatitis B and C virus
 - Hepatitis B virus (regardless of HCV)
 - Hepatitis C virus (regardless of HBV)
 - Alcoholism
 - Cirrhosis
 - Nonalcoholic Steatohepatitis (NASH)
 - Non-alcoholic fatty liver disease (NAFLD)
 - Other

- Hepatitis B virus surface antigen (HBsAg), Hepatitis B virus core antibody (HBCAB) and HCV laboratory results summary
 - HBsAg (+) , HBCAB(+)
 - HBsAg (+) , HBCAB(-)
 - HBsAg (-) , HBCAB(+)
 - HBsAg (-) , HBCAB(-)
 - HCV (+)
 - HCV (-)
- BCLC Grade (See XL184-312 Protocol Appendix J)
 - 0 (Very Early Stage)
 - A (Early Stage)
 - B (Intermediate Stage)
 - C (Advanced Stage)
 - D (Terminal Stage)
- Child-Pugh Grade (See XL184-312 Protocol Appendix K)
 - A (score 5 - 6)
 - B (score 7 – 9)
 - C (score 10 – 15)
- Hepatic Encephalopathy Status for Child-Pugh Grade
 - None
 - Grade I-II
 - Grade III-IV
 - Missing or unknown
- Ascites Status for Child-Pugh Grade
 - Absent
 - Slight
 - Moderate
 - Tense
 - Missing or unknown
- Time in years to randomization since initial diagnosis of HCC (Note: Incomplete diagnosis dates will be imputed as detailed in Appendix A)
- Currently has metastatic disease per investigator (Yes, No)
- Current Extent of HCC Disease per CRF:
 - Portal Vein Invasion (Yes, No, Unknown)
 - Bile Duct Invasion (Yes, No, Unknown)
 - Macrovascular Invasion (Yes, No, Unknown)

- Extrahepatic Disease (Yes, No, Unknown)
 - Other (Yes, No)
- Summaries for tumor assessment at screening per Investigator and BIRC are:
 - Extent of disease per target/non-target lesions
 - Liver
 - Bone
 - Lymph nodes
 - Important visceral sites
 - Adrenal gland
 - Lungs
 - All other sites
 - Incidence of all other sites will be individually reported
 - Number of target lesions (1, 2, ≥ 3)
 - Descriptive statistics for sum of target lesion diameter
 - Has measurable disease (Yes, No)
 - Number of organs with lesions at screening (1, 2, ≥ 3)
- PD-L1 immunohistochemistry status (High, Low/Negative, Unknown)

5.6 Baseline Laboratory Values

Frequencies and percentages will be provided for baseline laboratory values for selected laboratory parameters specified below for the PITT and ITT populations.

- Alpha-fetoprotein (AFP) (ng/mL)
 - <400
 - ≥ 400
- Prothrombin INR
 - ≤ 2.3
 - >2.3
- Serum albumin (g/L)
 - <35
 - ≥ 35

- Total bilirubin (μmol/L)
 - <22.23
 - $\geq 22.23 - < 29.07$
 - ≥ 29.07
- Platelets ($10^9/L$)
 - <80
 - ≥ 80
- ANC/lymphocyte ratio
 - <3
 - ≥ 3
- ALBI grade

ALBI grade will be defined based on the calculated ALBI score. ALBI Grade =1 if ALBI score ≤ -2.60 , ALBI Grade=2 if ALBI score > -2.60 to ≤ -1.39 , ALBI Grade=3 if ALBI score > -1.39 .

ALBI Score = $(\log_{10} \text{bilirubin}[\mu\text{mol/L}] \times 0.66) + (\text{albumin}[\text{g/L}] \times (-0.0852))$

- 1
- 2
- 3

6 TREATMENTS AND MEDICATIONS

6.1 Prior Non-Radiation Anticancer Therapy

The study aims to enroll subjects who have not received previous systemic anticancer therapy for advanced HCC including chemotherapy, small molecule kinase inhibitors, and immune checkpoint inhibitors (ICI). Subjects who have received local intra-tumoral or arterial chemotherapy are eligible.

The following will be summarized categorically or with descriptive statistics as appropriate for all subjects in the ITT, PITT, Safety and P-Safety populations:

- The time from the end of most-recent local non-radiation anticancer regimen for advanced HCC to randomization will be summarized descriptively
- Number of prior local non-radiation anticancer regimens (e.g. TACEs) for advanced HCC per subject (1, 2, ≥ 3) and descriptive statistics

All prior local non-radiation anticancer agents will be summarized categorically by Anatomical Therapeutic Chemical (ATC) Class Text and WHO-DD base substance preferred name by study treatment arm and context of therapy (HCC - Local, HCC – Neoadjuvant, HCC – Adjuvant, and Other). All prior systemic non-radiation anticancer agents will also be summarized, primarily to demonstrate that there were no subjects in the study who received such therapy.

6.2 Prior Radiation Therapy

Data obtained from the history of radiation therapy CRF will be summarized categorically or with descriptive statistics as appropriate for all subjects in the ITT, PITT, and Safety populations:

- Number of prior radiation therapies for HCC per subject (1, 2, ≥ 3) and descriptive statistics
- Subject incidence of radiation therapy by indication (HCC and Other)
- Subject incidence of radiation therapy by type (External beam radiation therapy [EBRT], Internal radiation therapy [Brachytherapy], Radioisotope therapy, Radioembolization, and Other) for HCC or Other indications
- Subject incidence of radiation therapy by site (Bone, Soft-tissue, Unknown) for HCC or Other indications
- Number and percent of subjects that received radiation by anatomic sites

6.3 Prior and Concomitant Medications (Excluding Anticancer Therapy)

Medications recorded on the CRFs will be coded using the WHO-DD. Prior and concomitant medications, other than prior and subsequent anticancer therapies, will be summarized by treatment group in the P-Safety and Safety populations by ATC and WHO-DD base substance preferred name. In addition, prior medications will also be summarized in the PITT and ITT populations by ATC and WHO-DD base substance preferred name. A listing of anti-viral therapies will be provided for the Safety population. Anticancer therapies are addressed in Sections 6.8 and 6.9 of this plan.

6.4 Subsequent Immune Modulating Medications

Immune modulating medications (IMMs) are selected medications with immune-modulating effects that may be used to manage immune-related AEs that result from treatment with atezolizumab. A list of the verbatim terms for these medications will be identified and provided along with the ATC and WHO-DD base substance preferred name. The incidence of subsequent

IMM and high-dose IMM (defined as ≥ 40 mg/day of prednisone or equivalent) for AESIs will be summarized by treatment group in the Safety and P-Safety populations by ATC and WHO-DD base substance preferred name.

6.5 Study Treatment Exposure

Study treatment exposure will be summarized descriptively and will include subjects in the P-Safety and Safety populations. Due to different treatment types (infusion vs. oral tablet) and frequency of administration (q3wk vs daily) between atezolizumab and cabozantinib, the exposure summaries for cabozantinib and atezolizumab will be presented separately along with summary for study treatment exposure. The study protocol allows subjects on the combination treatment to discontinue one component of the combination treatment but continue to receive the other component. Date of discontinuation along with reason for discontinuation will be recorded on separate CRFs for cabozantinib and atezolizumab treatment components. Duration of cabozantinib is defined as time from first dose to date of decision to discontinue and duration of atezolizumab is defined as time from first dose to date of last dose. Inclusion of the various treatment arms in the presentation of exposure summaries are described in Section 4.6.

For the combination regimen (experimental arm) an overall summary will be provided as follows:

- Duration (in months) of exposure, defined as maximum of duration of cabozantinib exposure and duration of atezolizumab exposure, calculated as maximum of [(date of decision to discontinue cabozantinib/cut-off date – date of first dose of cabozantinib + 1) /30.4375 and (last dose date of atezolizumab – date of first dose of atezolizumab + 1) /30.4375]
- The number and percent of subjects for who received at least one non-zero dose of cabozantinib > 4 weeks after last dose of atezolizumab.
- The number and percent of subjects for who received at least one dose of atezolizumab > 4 weeks after non-zero dose of cabozantinib.

The other summaries for cabozantinib and atezolizumab given in combination will present each agent separately as the former is an oral drug and the latter is an infusion drug.

The following independent summaries will be provided for cabozantinib 40 mg (as part of combination), cabozantinib 60 mg (as a single agent) and sorafenib. The start and end dates refer to the respective individual agent.

- Duration (in months) of exposure, including dose holds, calculated as (date of decision to discontinue study treatment/cut-off date – date of first dose + 1) /30.4375
- Average daily dose (mg/day) of study treatment, calculated as (total mg received / duration of exposure in days)
- Percent dose intensity, calculated as $100 * (\text{average dose in mg/day}) / (40 \text{ mg/day})$ for cabozantinib in experimental arm
- Percent dose intensity, calculated as $100 * (\text{average dose in mg/day}) / (60 \text{ mg/day})$ for cabozantinib in single agent arm
- Percent dose intensity, calculated as $100 * (\text{average dose in mg/day}) / (800 \text{ mg/day})$ for sorafenib (control arm).
- Duration (in months) of exposure, excluding dose holds, defined as (date of decision to discontinue study treatment – date of first dose – total days with dose received of 0 mg during this interval + 1) /30.4375
- The last dose level received (with or without dose holds)

Summaries for atezolizumab (experimental arm):

- Duration of exposure calculated as (last dose date infusion of atezolizumab – date of first dose of atezolizumab +1)/30.4375
- Number of infusions of atezolizumab received
- Number of expected infusions of atezolizumab defined as duration of exposure divided by 21
- Number of actual infusions / Number of expected infusions
- Average dose (mg/infusion) of atezolizumab treatment received, calculated as (total mg received / # of infusions of atezolizumab received.)
- Percent dose intensity calculated as $100 * (\text{total mg received}) / ((\text{last dose date} - \text{first dose date} + 21) * (1200 / 21))$

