Required safety assessments are to be performed on a schedule based on the date of the first dose (W1D1) and every 3 weeks (\pm 3 days) (ie, W4D1, W7D1, W10D1, etc). For subjects in the combination arm, required safety assessments may occur outside the protocol-defined windows due to safety-driven delays in atezolizumab administration and will not be considered protocol deviations as long as required safety assessments are performed at least every 3 weeks (\pm 3 days). See the CRF completion guidelines for instructions on how to enter study data in such circumstances. The following are the reminders:

- Doses of atezolizumab must not be given less than 19 days apart (see [Section 6.2.4](#)).
- Specific laboratory tests are required to be performed and evaluated within 72 hours prior to each administration of atezolizumab (see [Section 5.8.5](#)).
- The tumor assessment and HRQOL schedules are to be maintained relative to the date of first dose of study treatment (or randomization date for subjects never treated) irrespective of the dates of safety assessments.
- PK and biomarker sample collection schedules are per schedule of assessments ([Appendix A](#) and [Appendix B](#)).

Safety follow-up visits will be performed 30 (+14) days (FU-1) and approximately 100 days (\pm 14 days) (FU-2) after the date of the decision to permanently discontinue study treatment (see [Section 8.4](#)).

If study treatment is held due to AEs, investigators should perform additional safety assessments weekly (or more frequently as clinically indicated).

Radiographic tumor assessments should be performed as described in [Section 5.8.6](#), and HRQOL assessments should be performed as described in [Section 5.8.8](#). The schedule of assessments should be maintained regardless of whether study treatment is given, reduced, held or discontinued until a criterion for discontinuation of radiographic assessments is met (see [Section 5.8.6.2](#)).

In accordance with the ITT principle, HRQOL, radiographic tumor assessments, and survival follow-up are to be performed per protocol even for subjects randomized who never receive study treatment. For such subjects, W1D1 is defined as the date of randomization.

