6.2.4. Study Drug Administration on Week 1 Day 1 (W1D1)

The first dose of study treatment should occur as soon as possible after randomization. The date of the first dose of study treatment is defined as W1D1. The first doses of all study treatments are to be administered at the clinic.

Cabozantinib:

For subjects receiving cabozantinib (experimental arm and single-agent cabozantinib arm), subjects will fast (with the exception of water) for at least 2 hours before receiving cabozantinib. Upon completion of the 2-hour fast, the subject will receive the oral dose of cabozantinib with a minimum of 8 oz (240 mL) of water in the clinic and then the subject will continue to fast for 1 hour while under observation at the clinic. For subjects on the experimental arm (cabozantinib and atezolizumab), atezolizumab is to be administered first. For cabozantinib dosing on subsequent dosing days refer to [Section 6.2.5](#).

Atezolizumab:

Doses of atezolizumab will be administered intravenously at the clinic by infusion every 3 weeks (\pm 2 days).

The infusion of atezolizumab (1200 mg fixed dose) will be prepared according to local prescribing information or the pharmacy manual. The IV administration of atezolizumab can only occur in a clinical setting with staff experienced in managing of infusion-related reactions (IRRs) and with access to emergency services. The initial IV infusion of atezolizumab will be given over 60 min (\pm 15 min) without premedication for potential IRRs or CRS. Subsequent IV infusions may be given over 30 min (\pm 10 min) if the initial infusion is tolerated. Premedication

for IRRs or CRS is allowed after the initial infusion. No bolus or IV push of atezolizumab is allowed. Dose delays will be allowed for toxicities suspected to be due to atezolizumab administration. Atezolizumab infusion requirements and guidance are summarized in [Table 6](#).

Table 6: Atezolizumab Infusion Requirements and Guidance

First Infusion	Subsequent Infusions

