Cabozantinib dosing (Sections 6.2.1, 6.2.3, 6.2.4, and 6.2.5)			
Experimental Arm: Cabozantinib tablets given on W1D1 after atezolizumab infusion. Taken once daily at home thereafter until study treatment is discontinued.
 
Single-Agent Cabozantinib Arm: Cabozantinib tablets given in the clinic on W1D1. Taken once daily at home thereafter until study treatment is discontinued.
													
Sorafenib dosing (Sections 6.2.2, 6.2.4, and 6.2.6)			
Control Arm: First sorafenib dose (tablets) given on W1D1 in the clinic. Taken twice daily at home thereafter until study treatment discontinued
													
Atezolizumab dosing (Section 6.1.1.2)			Doses of atezolizumab will be administered intravenously at the clinic by infusion every 3 weeks (± 2 days). Atezolizumab dosing days may not necessarily align with safety assessment visits.													
Dispense/return of oral study drug and compliance accounting (Sections 6.4 and 6.5) ^b			X	X	X	X	X	Every 3 weeks (W16D1, W19D1 etc)								
Additional anticancer treatment and survival status (Section 5.8.13)			All treated subjects will be contacted at each post-treatment visit, including FU-1, FU-2, and every 12 weeks (± 14 days) after FU-2 visit until death. Any subjects who are randomized but not treated will be contacted every 12 weeks post-randomization until death													

^a Results of screening assessments must be reviewed before randomization to confirm that the subject meets the eligibility criteria.

^b Informed consent may be obtained greater than 28 days prior to randomization, but must be provided before any study-specific procedures are performed; however evaluations performed as part of routine care prior to informed consent can be utilized as screening evaluations if permitted by the site's IRB/EC policies.

^c Additional ECGs should be performed if clinically indicated.

^d This assessment is intended to confirm suitability for treatment after randomization. If this assessment has been performed during screening within 14 days (7 days for pregnancy test) prior to first dose (W1D1), this assessment does not need to be performed on W1D1 unless the subject's clinical status has changed (eg, onset of new symptoms indicative of clinical deterioration). If the assessment is performed on W1D1, the results must be available to and reviewed by the investigator prior to any treatment being administered.

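### SAP 6.5: the count of subjects given atezolizumab after cabozantinib omits the word *last*, so read literally it does not show single-component continuation

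*SAP*

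**What the plan says.** SAP 6.5 (Study Treatment Exposure) notes that combination-arm subjects may "discontinue one component of the combination treatment but continue to receive the other component". It then lists an overall summary for the combination regimen, to be produced in the Safety and P-Safety populations. Two of its bullets give the number and percent of subjects who:

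- "received at least one non-zero dose of cabozantinib > 4 weeks after last dose of atezolizumab"
- "received at least one dose of atezolizumab > 4 weeks after non-zero dose of cabozantinib"

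The first is tied to the last dose of the other agent. The second, which says only "after non-zero dose of cabozantinib", is not tied to any particular cabozantinib dose.

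No other text supplies the missing anchor. SAP 4.2 defines first and last dose for the combination taken as a whole. SAP 4.3 defines a last-dose date for each agent, but this bullet does not call on it. The SAP addendum deals only with information fractions and event counts that exceed plan.

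**The concern.** The two bullets look like mirror images, meant to identify subjects who went on with one agent after the other had stopped. That intent is inferred from the sentence introducing them and from the wording of the first bullet; the SAP does not state it.

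Cabozantinib is taken daily from the day of the first infusion. Any infusion given more than 28 days into treatment therefore follows some non-zero cabozantinib dose by more than 4 weeks, even in a subject who took cabozantinib without a break. Programmed that way, the second row would mostly record who reached a third infusion, while the row above it recorded genuine continuation of cabozantinib alone. A reader would take the two as comparable, and they would not be.

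**Working it through.** The plan states no expected value for this count, so there is no figure to reproduce. The check is date arithmetic on the dosing schedule.

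**Inputs**

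- Start of cabozantinib in the experimental arm, Protocol Appendix A: "Cabozantinib tablets given on W1D1 after atezolizumab infusion", then once daily. Count this as day 0 for both agents.
- Infusion interval, Protocol 6.2.4: "Doses of atezolizumab will be administered intravenously at the clinic by infusion every 3 weeks", with a window of plus or minus 2 days, so 21 days nominal and 23 at the upper window.
- Minimum interval, Protocol 5.2: "Doses of atezolizumab must not be given less than 19 days apart".
- Threshold in SAP 6.5: more than 4 weeks = more than 28 days.

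**Step 1: when the literal criterion is first met.** Infusion k falls (k − 1) × gap days after the first cabozantinib dose.

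| Gap (days) | Infusion 2 | Infusion 3 | Infusion 3 > 28? |
|---|---|---|---|
| 19 | 19 | 2 × 19 = 38 | yes |
| 21 | 21 | 2 × 21 = 42 | yes |
| 23 | 23 | 2 × 23 = 46 | yes |

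With a W1D1 start, two on-schedule infusions never qualify and three always do. A subject with two infusions also qualifies if the second is delayed to day 29 or later.

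**Step 2: who escapes at the third infusion.** If cabozantinib starts L days after infusion 1, the criterion needs 2 × gap − L > 28, so L can be at most 2 × gap − 29. That is 9 days at a 19-day gap, 13 at 21 and 17 at 23. Subjects who start later than this, or who never take cabozantinib, are not counted at infusion 3. Late starts are possible: Protocol 6.2.4 has cabozantinib delayed after an infusion reaction or cytokine release syndrome until recovery.

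**Step 3: three readings on example histories.** Infusions are on days 0, 21, 42, 63, 84, 105, 126 and 147.

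| Cabozantinib history | Any earlier dose | Most recent earlier dose | Last dose |
|---|---|---|---|
| Daily throughout | counted | not counted | not counted |
| Held days 61 to 110, then resumed to beyond day 147 | counted | counted (105 − 60 = 45) | not counted |
| Stopped for good, last dose day 60 | counted | counted (105 − 60 = 45) | counted (105 − 60 = 45) |

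Only the last-dose reading isolates the subject who stopped cabozantinib and continued atezolizumab. The any-dose reading does not separate the three at all.

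**Step 4: how large the literal percentage might be.** The documents give no distribution of infusions, only an average of about 6 months on treatment, not split by arm (Protocol 3.2). That is 6 × 30.4375 / 21 ≈ 8.7 intervals. Purely as an assumption, take exponential time on treatment with that mean (182.6 days). The share still on treatment at day 42 is exp(−42/182.6) ≈ 79%. With means of 4 and 8 months it is exp(−42/121.75) ≈ 71% and exp(−42/243.5) ≈ 84%. These figures illustrate a majority; they are not estimates from the plan.

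**The case against.** The strongest reply is that the meaning is evident. The paired bullet says *last*, the introducing sentence describes stopping one component, and the second bullet does not say *any* or *first* dose either. A careful programmer would probably supply the word. This stands as far as it goes: it is a wording slip, and the any-dose result is one of at least three readings. But a specification programmed under contract (SAP 1) should not leave that choice open, and the readings give different counts.

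It can also be said that single-component continuation is visible elsewhere. SAP 5.2 summarises reasons for discontinuing each study treatment and describes combination-arm subjects who stop components because of an adverse event. SAP 8.1 tabulates adverse events leading to discontinuation of the oral or the IV agent only, and SAP 6.5 gives exposure duration by agent. This limits the importance. None of these, however, reproduces the count of subjects actually dosed with one agent more than 4 weeks after the other, whatever the reason.

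Three stronger inferences are tempting, and the documents do not support them:

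- That the row would come out close to 100%. The denominator includes subjects with one or two infusions, and the infusion distribution is not given.
- That every subject infused at W7D1 or later qualifies. Subjects who never took cabozantinib, or started it late, can escape.
- That the assessment of component contribution is compromised. Protocol 1.5.2 rests cabozantinib's contribution on the PFS comparison of single-agent cabozantinib with sorafenib, not on this exposure count.

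**Conclusion.** The point holds as a drafting error in one descriptive rule. Read as any earlier dose, the bullet counts nearly all subjects who started cabozantinib on W1D1 and received three or more infusions (third infusion 38 to 46 days after the first cabozantinib dose), whether or not cabozantinib was stopped. It then fails to measure single-component continuation. The proportion of the arm affected is probably a majority but cannot be stated from the documents.

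The conclusion assumes that infusions keep to the protocol's spacing and that the two bullets were meant as a symmetric pair. The importance is minor: one exposure summary changes, and no hypothesis test, alpha, event count or sample size is touched.

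**What to change.** In SAP 6.5, insert *last* in the second bullet, so that it counts subjects with at least one atezolizumab dose more than 4 weeks after the last non-zero dose of cabozantinib. This matches the bullet above it. If atezolizumab given during long cabozantinib holds is also of interest, it should be a separate, named row.

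The cost is one word. SAP 4.9 already allows clarifications and minor corrections through an addendum approved before the final study analyses. No new data are needed, because dosing intervals and infusion dates are already collected (Protocol 6.4).

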4 GENERAL CONVENTIONS

The statistical principles applied in the design and planned analyses of this study are consistent with International Conference on Harmonization (ICH) E9 (ICH Harmonized Guideline E9 Statistical Principles for Clinical Trials, 1998) and draft E9 R1 guidelines (ICH Harmonized Guideline E9 (R1) Statistical Principles for Clinical Trials: Addendum: Estimands and Sensitivity Analysis in Clinical Trials (Draft), 2017).

Continuous data will be summarized using descriptive statistics (number of observations, mean, standard deviation, median, 25th and 75th percentiles, minimum, and maximum). Frequencies and percentages will be used for summarizing categorical (discrete) data.

Confidence intervals, when presented, will generally be constructed at the 95% level. For binomial variables, the Clopper-Pearson method (Clopper CJ, 1934) may be employed unless otherwise specified.

A month is operationally defined to be 30.4375 days. Six months is operationally defined to be 183 days.

Efficacy summaries will be presented by treatment arm randomized to and safety summaries by treatment received unless otherwise specified.

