8.4 Laboratory Assessments

8.4.1 Variables

The following treatment-emergent laboratory abnormalities will be summarized. A treatment emergent laboratory abnormality is defined as any laboratory abnormality with an onset date on or after the date of the first dose of study drug.

Category	Abnormality	SDTM LBTESTCD	Grading System
Hematology	WBC decreased	WBC	CTCAE
	ANC decreased	NEUT	CTCAE
	Lymphocytes increased Lymphocytes decreased	LYM	CTCAE
	Platelets decreased	PLAT	CTCAE
	Hemoglobin increased Hemoglobin decreased	HGB	CTCAE
Serum chemistry	Albumin decreased	ALB	CTCAE
	ALP increased	ALP	CTCAE
	Amylase increased	AMYLASE	CTCAE
	ALT increased	ALT	CTCAE
	AST increased	AST	CTCAE
	Calcium, corr increased Calcium, corr decreased	CACORR	CTCAE
	Creatinine increased	CREAT	CTCAE
	GGT increased	GGT	CTCAE

Category	Abnormality	SDTM LBTESTCD	Grading System
	Glucose increased Glucose decreased	GLUC	CTCAE
	LDH increased	LDH	Sponsor
	Lipase increased	LIPASE	CTCAE
	Magnesium increased Magnesium decreased	MG	CTCAE
	Phosphate decrease	PHOS	CTCAE
	Potassium increased Potassium decreased	K	CTCAE
	Sodium increased Sodium decreased	NA	CTCAE
	Total bilirubin increased	BILI	CTCAE
	Uric acid increased ²	CYURIAC	CTCAE
Urine chemistry	UPCR increased	PROTCRT	Sponsor
Endocrinology ¹	Thyroid Stimulating Hormone increased Thyroid Stimulating Hormone decreased	TSH	HLN

¹ TSH is held in the SDTM "chemistry" laboratory category; will use HLN = high, low, normal classification based on normal range

² Uric acid increases will be graded only as Grade 1 or Grade 4. Grade 2 is not defined per CTCAE v4 and Grade 3 cannot be distinguished from Grade 1 based upon the result alone.

Sponsor-defined grades are to be applied to the following analytes:

LDH:

- Grade 1 if $>$ ULN to $\leq 2 \times$ ULN
- Grade 2 if $> 2 \times$ ULN to $\leq 3 \times$ ULN
- Grade 3 if $> 3 \times$ ULN

UPCR:

- Grade 1 if ≥ 17.0 to ≤ 121.0 mg/mmol (≥ 0.15 to ≤ 1.0 mg/mg)
- Grade 2 if > 121.0 to ≤ 396.0 mg/mmol (> 1.0 to < 3.5 mg/mg)
- Grade 3 if > 396.0 mg/mmol (> 3.5 mg/mg)

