$eGFR = 186 \times (\text{Creatinine in mmol per L} / 88.4)^{-1.154} \times (\text{Age})^{-0.203} \times (0.742 \text{ if female}) \times (1.210 \text{ if black})$ [from the UK CKD eGuide on the Renal Association website: <http://egfrcalc.renal.org/>]

C. Categorical summaries for baseline status for TSH and Free T4 will be presented. In addition, categorical summaries for post-baseline TSH and Free T4 status among subjects with TSH and Free T4 in the normal range at baseline will also be presented.

For descriptive summaries of change from baseline in continuous laboratory variables, only central lab results will be considered. For analyses of shift in grade from baseline or worst grade after baseline, all available results will be considered regardless of whether from the central or local lab.

Summary Type	Include central lab results?	Include local lab results?
Subject-Incidence of Treatment Emergent Laboratory Abnormalities in Selected Laboratory Tests by CTCAE Grade	Y	Y
Change from Baseline in Laboratory Values	Y	N
Shift from Baseline in Laboratory Values by CTCAE Grade	Y	Y
Worsening Shift of at Least 2 Grades from Baseline in Selected Laboratory Tests	Y	Y
Shift from Baseline in Laboratory Values by High/Low/Normal	Y	Y
Shift from Baseline in Laboratory Values by Sponsor-defined Grades	Y	Y
Laboratory Abnormalities with a subject-incidence of $\geq 5\%$ (All Grades) or $\geq 2\%$ (Grades 3-4) in either arm	Y	Y
Laboratory Abnormalities with a subject-incidence of $\geq 5\%$ (All Grades) or $\geq 2\%$ (Grades 3-4) in the experimental arm	Y	Y
Laboratory Abnormalities with an increase in subject-incidence of $\geq 5\%$ (All Grades) or $\geq 2\%$ (Grades 3-4) in the experimental arm	Y	Y

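### SAP 6.5 undercounts expected atezolizumab infusions by almost one cycle, so patients dosed exactly every 21 days score above 100% on the actual/expected ratio; one eGFR unit and one UPCR cut-off also need correcting

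*SAP*

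**What the plan says.** **Infusions.** For atezolizumab, SAP 6.5 gives "Duration of exposure calculated as (last dose date infusion of atezolizumab – date of first dose of atezolizumab +1)/30.4375". Section 4 confirms the unit: "A month is operationally defined to be 30.4375 days". The list then has "Number of expected infusions of atezolizumab defined as duration of exposure divided by 21", followed by the reported summary "Number of actual infusions / Number of expected infusions". The last bullet of the list, percent dose intensity, divides total mg received by (last dose date - first dose date + 21) × 1200/21. The protocol (Section 6.2.4) schedules infusions every 3 weeks, ± 2 days.

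**eGFR.** SAP 8.4.2 divides "Creatinine in mmol per L" by 88.4 in the formula behind the renal failure screen. The SI version of the Cockcroft-Gault formula in protocol Table 3 takes creatinine in µmol/L.

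**UPCR.** In the sponsor-defined grades of SAP 8.4.1, Grade 1 ends at 121.0 mg/mmol, equated with 1.0 mg/mg, and the next line begins "Grade 2 if > 121.0 to". The protocol equates 1 mg/mg with 113.2 mg/mmol (inclusion criterion 10j) and 113.1 mg/mmol (Table 14).

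**The concern.** The expected count has two separate faults. The duration it starts from is in months, while the divisor of 21 only makes sense in days. That duration also stops on the day of the last infusion, so the final 21-day cycle contributes one day, yet the numerator counts its infusion in full. A summary meant to read 100% for on-schedule dosing would then sit above 100%, by most in patients who stop early, and a single skipped dose could be absorbed. Two lines of the same exposure table would disagree about the same patients.

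The other two items are of the same kind: a derivation that, programmed as written, gives a figure at odds with the protocol or with the SAP's own neighbouring values.

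**Working it through.** **1. Infusion ratio.** The plan states no expected number, only formulas. The internal benchmark is its own dose intensity formula. For n infusions of 1200 mg exactly 21 days apart, last - first = 21(n-1), so dose intensity = 1200n / {[21(n-1) + 21] × 1200/21} = 100% for every n.

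For the same patients, the SAP's expected count is:
- days reading: [21(n-1) + 1]/21
- literal (months) reading: {[21(n-1) + 1]/30.4375}/21

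| n | Days, first to last + 1 | Expected (days reading) | Actual/expected (days) | Actual/expected (literal) | Using (last - first + 21)/21 |
|---|---|---|---|---|---|
| 1 | 1 | 0.048 | 21.0 | 639 | 1.00 |
| 2 | 22 | 1.048 | 1.91 | 58 | 1.00 |
| 4 | 64 | 3.048 | 1.31 | 40 | 1.00 |
| 9 | 169 | 8.048 | 1.12 | 34 | 1.00 |
| 18 | 358 | 17.048 | 1.06 | 32 | 1.00 |
| 35 | 715 | 34.048 | 1.03 | 31 | 1.00 |

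The protocol expects about 6 months on treatment, which is 6 × 30.4375/21 = 8.7 cycles, so the nine-infusion row is close to the average duration.

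*Skipped dose.* Ten infusions are scheduled and one in mid-course is missed: 9 infusions, last - first = 189 days. SAP ratio, days reading: 9/(190/21) = 9/9.048 = 0.995. With the +21 span: 9/(210/21) = 0.90. SAP percent dose intensity: 9 × 1200/(210 × 1200/21) = 90%.

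*Edge of the visit window.* If every interval is 23 days, the days-reading ratio is 21n/[23(n-1) + 1] = 21n/(23n - 22). This is 231/231 = 1.00 at n = 11 and 252/254 = 0.992 at n = 12. With the +21 span, n = 12 gives 252/(23 × 11 + 21) = 252/274 = 0.92, so the SAP value is still too high.

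**2. eGFR.** Check on the constant: protocol Table 3 for males uses a divisor of 72 with mg/dL and a multiplier of 1.23 with µmol/L, which implies 72 × 1.23 = 88.6 µmol/L per mg/dL. So 88.4 is a µmol/L conversion. Entering mmol/L inflates eGFR by 1000^1.154 = 2,897. Example (assumed patient: male, not black, age 60, creatinine 300 µmol/L): 186 × (300/88.4)^-1.154 × 60^-0.203 = 19.8; with 0.300 entered, about 57,300. For an assumed male, not black, aged 65, an eGFR of 30 needs an input of about 206. Read as mmol/L that is 206,000 µmol/L, so the eGFR < 30 limb cannot be met.

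**3. UPCR.** Conversion factor implied by each SAP cut-off: 17.0/0.15 = 113.3; 396.0/3.5 = 113.1; 121.0/1.0 = 121.0. The outer two reproduce the protocol's 113.1-113.2 and the middle one does not. 121.0/113.1 = 1.07, about 7% too high. Values from about 113 to 121 mg/mmol are Grade 1 on the SAP's mg/mmol scale and Grade 2 on its mg/mg scale.

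**The case against.** Several stronger inferences are tempting, and the documents do not support them.

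- *That atezolizumab exposure becomes unreadable, or skipped doses are hidden.* The same list reports infusions received, average mg per infusion and a correctly spanned dose intensity, which shows 90% in the skipped-dose example. SAP 6.6 also tabulates delays due to adverse events by number and duration. Only the infusion ratio is compromised.
- *That every compliant patient appears over-treated.* Compliance allows ± 2 days. At constant 23-day spacing, the days-reading ratio is 1.00 at 11 infusions and below 1 from 12. The statement above holds for exact 21-day spacing, and the excess shrinks with longer treatment.
- *That ratios of 31 to 639 would be published.* A programmer would probably see that 21 is in days; SAP 6.5 asks for duration in days explicitly when defining average daily dose. The literal reading is a wording fault and should not carry the size of the problem.
- *That the renal screen fails.* Three criteria are joined by or. The creatinine criterion (at least 3.0 × ULN and 2.0 × baseline) does not use eGFR, and in eGFR at or below 50% of baseline the unit cancels. The mmol may be a plain slip for µmol, or a lost character: the ferritin limits in protocol 6.6.2.2.13 pair mg/L with the same number in ng/mL, which is a similar pattern.
- *That UPCR is in the wrong units.* The units are right and one cut-off is mis-converted. These are summary grades. Protocol Table 14 calls for no treatment change up to 2 mg/mg, so for values of 1.00-1.07 mg/mg the grade disagreement implies no different dose action.

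All of this limits the consequences. None of it makes the expected-infusion formula right: it still conflicts with the bullet beside it, and the SAP addendum, which deals only with analyses run on more information or events than planned, does not correct any of the three.

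**Conclusion.** The expected-infusion definition is wrong as written. On the days reading it loses 20 of 21 days of the last cycle, so the ratio under exact 21-day dosing is 21.0 at one infusion, 1.12 at nine and 1.03 at 35, where 1.00 is correct; one missed dose in ten reads 0.995 where 0.90 is correct. These figures assume exact 21-day spacing apart from the missed dose. The eGFR unit and the 121.0 mg/mmol cut-off are real but smaller errors: one inert limb out of three, and one boundary about 7% too high. All three belong to descriptive exposure or safety summaries. SAP Section 8 plans no formal safety comparison between the experimental and control arms, and nothing here reaches the PFS or OS tests or the alpha allocation. The point is worth correcting because a programmer must otherwise either follow the text to a wrong number or depart from it without a record.

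**What to change.** Make three one-line changes to the SAP:

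1. Section 6.5: expected infusions = (last infusion date - first infusion date + 21)/21, in days. This matches the dose intensity span and returns exactly 1.00 for on-schedule dosing.
2. Section 8.4.2: state creatinine in µmol/L in the eGFR formula, after checking the signed copy for a lost character.
3. Section 8.4.1: reconcile the 121.0 mg/mmol boundary between Grades 1 and 2 with the protocol's conversion of 1 mg/mg (113.1-113.2 mg/mmol), using one factor throughout. This concerns the tabulated grade only, not any management threshold.

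SAP 4.9 already provides for minor corrections by addendum. The cost is a short addendum and a check of the derivation programs, with no new data, no burden on patients and no effect on alpha.
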